16.2.4 Progression Free Survival

The PFS time, according to the RECIST 1.1, is defined as time from first administration of study treatment to the date of the first documentation of objective PD or death due to any cause, whichever occurs first.

PFS time (in months) is defined as:

$$(\text{date of event or censoring} - \text{date of first dose of study treatment} + 1) / 30.4375$$

PFS data will be censored on the date of the last adequate tumor assessment for subjects who do not have an event (PD or death), for subjects who start a new anti-cancer therapy prior to an event or for subjects with an event after two or more missing tumor assessments. Subjects who do not have a baseline tumor assessment or who do not have any post-baseline tumor assessments will be censored on the date of the first study treatment unless death occurred on or before the time of the second planned tumor assessment in which case death will be considered an event. Details on determination of the first disease progression date are specified in the IERC charter.

If a tumor assessment was performed on the same day as the start of a new anti-cancer therapy, it will be assumed that the tumor assessment was performed prior to the start of the new anti-cancer therapy; therefore, this tumor assessment will be included in the derivation of the PFS time.

The censoring and event date options to be considered for the PFS and DR analysis are presented in [Table 4](#). Last adequate tumor assessment is defined as tumor assessment result that is not “NE” or “NA”.

Table 4 Outcome and Event Dates for PFS and DR Analyses

| Scenario | Date of event / censoring | Outcome |
|--|--|---|
| No baseline assessment | Date of first study treatment | Censored ^a |
| Progression or death \leq xx weeks after last tumor assessment or \leq xx weeks after treatment start date, where xx is 12 weeks through 12 months from start of treatment, and 24 weeks thereafter. | Date of progression or death | Event |
| Progression or death $>$ xx weeks after the last tumor assessment, where xx is 12 weeks through 12 months from start of treatment, and 24 weeks thereafter. | Date of last adequate tumor assessment | Censored |
| No progression | Date of last adequate tumor assessment | Censored |
| Treatment discontinuation due to “Disease progression” without documented progression | Not applicable | Information collected on treatment discontinuation page is ignored since outcome should be derived based on documented progression only. General censoring rule is applied. |
| New anti-cancer therapy given | Date of last adequate tumor assessment before anti-cancer therapy is given | Censored |

^a However if the subject dies \leq 12 weeks after treatment start date the death is an event with date on death date.

The analysis of PFS will be performed using a Kaplan-Meier method with the same approach as for duration of response described in [Section 16.2.3](#). Kaplan-Meier estimates (product-limit estimates) will be presented together with a summary of associated statistics including corresponding two-sided 95% CIs. In particular, the proportion of PFS at 3, 6 and 12 months will be estimated with corresponding two-sided 95% CIs.

Frequency (number and percentage) of subjects with each event type (PD or death) and censoring reasons will be presented. Censoring reasons are as follows, presented in a hierarchical manner:

- No baseline assessment
- No post baseline assessments
- Start of new anti-cancer therapy
- Event after 2 or more missing assessments
- Withdrawal of consent to continuing tumor assessment
- Lost to follow-up
- Ongoing in the study without an event

The PFS time or censoring time and the reasons for censoring will also be presented in a subject listing.

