16.1 Primary Endpoint Analyses

Analysis sets: FAS / PP analysis set

The primary endpoint for Part B of this study is durable response, defined as objective response in terms of CR or PR according to RECIST 1.1, as determined by an IERC, with a duration of at least 6 months. The duration of response (DR) will be calculated as specified in [Section 16.2.3](#).

DRR is defined as the proportion of subjects with an objective response in terms of CR or PR according to RECIST 1.1, as determined by an IERC, with a duration of at least 6 months, among all subjects in the FAS.

For subjects with a confirmed response but neither documented disease progression nor death within 12 weeks after the last tumor assessment as of the cut-off date for the analysis, the DR will be censored at the date of the last tumor assessment. If the censored DR is less than 6 months, the subject will be treated as failure in the analysis of DRR. Otherwise, the subject will be considered as success and will be included in the numerator in the calculation of DRR.

The following requirement is taken into account for confirmation of response: PR or CR needs to be confirmed at a subsequent tumor assessment, preferably 6 weeks after the initial observation of response and according to the normal 6-week assessment schedule (or a subsequent assessment for PR), but no sooner than 5 weeks after the initial documentation of CR or PR.

DRR will be calculated along with the two-sided 95% CI using the Clopper-Pearson method (exact CI for a binomial proportion as computed by default by the FREQ procedure using the EXACT option). Assuming a true DRR of 45%, the probability to observe lower bound of the exact 95% confidence interval (CI) above 20% would be $> 99\%$ and above 30% would be 90%.

The primary endpoint analysis on FAS will be repeated for the PP analysis set as a sensitivity analysis if the PP analysis set includes less than 95% of subjects in the FAS.

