16.2.3 Duration of Response

DR is defined, for subjects with a confirmed objective response according to RECIST 1.1, as the time from first documentation of objective response (CR or PR) to the date of first documentation of objective PD or death due to any cause. If a subject has not had an event (PD or death), DR is censored at the date of last adequate tumor assessment. The censoring rules for DR are described in Section 16.2.4 for PFS.

DR (months) = (date of event or censoring – date of first objective response + 1)/30.4375

The Kaplan-Meier method will be used to estimate parameters for duration of response. Kaplan-Meier estimates (product-limit estimates) will be presented together with a summary of associated statistics including corresponding two-sided 95% CIs. In particular, the proportion of duration of responses at 3, 6 and 12 months will be estimated with corresponding two-sided 95% CIs. The CIs for the median will be calculated according to [Brookmeyer and Crowley \(2\)](#) and CIs for the survival function estimates at the above defined time points will be derived using the log-log transformation according to [Kalbfleisch and Prentice \(3\)](#) (CONFTYPE = loglog default option in SAS PROC LIFETEST). The estimate of the standard error will be computed using Greenwood's formula.

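### Part B missed-scan rule: the 12/24-week gap runs from the last scan, not the last adequate scan, so read literally a run of NE scans can turn a censored failure into a durable response

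*SAP*

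**What the plan says.** Part B SAP Section 16.2.4, Table 4, has two rows for a subject with PD or death: an event if the gap is within the window, censored if it is beyond. The censored row measures the gap as "xx weeks after the last tumor assessment, where xx is 12 weeks through 12 months from start of treatment, and 24 weeks thereafter". The event row uses the same starting point, or the start of treatment. The censoring date in that row is a different assessment, the last adequate one. Just above the table: "Last adequate tumor assessment is defined as tumor assessment result that is not" NE or NA. Protocol 8.3.2 makes the same distinction, and its Table 11 has the same wording.

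The text above Table 4 puts the rule another way. It censors at the last adequate assessment "for subjects with an event after two or more missing tumor assessments". It does not define missing or mention NE in that rule.

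The rule feeds the primary endpoint. Section 16.2.3 states: "The censoring rules for DR are described in Section 16.2.4 for PFS". Section 16.1 states: "The duration of response (DR) will be calculated as specified in" Section 16.2.3. It adds: "If the censored DR is less than 6 months, the subject will be treated as failure in the analysis of DRR"; a censored duration of 6 months or more is a success.

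Two further places bear on the point:

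- Section 16.1 gives its own censoring rule for responders without an event: "the DR will be censored at the date of the last tumor assessment". The duration-of-response paragraph in protocol 8.3.2 agrees with that. Section 16.2.3 and Table 4 use the last adequate assessment.
- Section 16.2.2, on best overall response, treats a PD as too late when it falls more than 12 weeks after first dose with no evaluable scan in between. There, NE scans do not shorten the gap.

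**The concern.** The rule exists so that a PD or death found after a long stretch without usable imaging is not credited as time in response. A scan rated NE gives no overall response, yet on the literal wording it restarts the window just as a PR scan would. Two responders with the same evaluable scans and the same PD date can then receive opposite primary outcomes, depending on whether the intervening scans were unreadable or not done.

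For DRR the direction is one-sided. The last adequate scan always precedes the event, so starting the gap there either leaves duration unchanged or replaces the event date with an earlier one. The literal rule can add durable responders and cannot remove any.

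Protocol 5.1 gives Part B a confirmatory role for some approvals. The only sensitivity analysis in Section 16.1 is the per-protocol repeat, and the per-protocol criteria do not address NE runs after response.

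**Working it through.** **Inputs.** Scans are at Week 7 and every 6 weeks, then every 12 weeks after Week 55 (protocol 7.1.2.2). Study day = (week − 1) × 7 + 1 (Part B SAP Section 11). Duration is ("date of event or censoring – date of first objective response + 1")/30.4375 months (Section 16.2.3). N = 112, with a two-sided 95% Clopper-Pearson interval (Sections 7 and 16.1). The historical reference is 11/62 = 17.7% (9.2 to 29.5).

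**The plan's own figures reproduce.** 32/112 gives 20.4 to 37.9, 45/112 gives 31.0 to 49.9, and 50/112 gives 35.2 to 54.3. At a true DRR of 45%, the probability of a lower limit above 20% is 0.9999 and above 30% is 0.9055 (stated: >99% and 90%).

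**Scan histories through Table 4 in year 1 (12-week window).** All first respond at Week 7 (day 43).

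| History | Gap from last scan | Literal result | Gap from last adequate scan | Result from last adequate scan |
|---|---|---|---|---|
| PR W7, 13, 19; NE W25, 31; PD W37 | 6 wk | event, 6.93 mo, success | 18 wk | censored W19, 2.79 mo, failure |
| Same, but W25 and W31 missed | 18 wk | censored W19, 2.79 mo, failure | 18 wk | same |
| PR W7, 13, 19; NE W25, 31; death W40 | 9 wk | event, 7.62 mo, success | 21 wk | censored W19, 2.79 mo, failure |
| PR W7, 13, 19, 25; NE W31; PD W37 | 6 wk | event, 6.93 mo, success | 12 wk | event, 6.93 mo, success |
| PR W7, 13, 19; NE W25, 31, 37; no event | n/a | censored W19, 2.79 mo, failure | n/a | same |

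Arithmetic:

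- PD at Week 37 is day 253: (253 − 43 + 1)/30.4375 = 211/30.4375 = 6.93.
- Week 19 is day 127: (127 − 43 + 1)/30.4375 = 85/30.4375 = 2.79.
- Death at Week 40 is day 274: 232/30.4375 = 7.62.

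The fourth row shows that a single NE scan changes nothing, because it leaves a gap of exactly 12 weeks, which is inside the window. Two consecutive NE scans are needed. The fifth row shows that under Table 4 trailing NE scans earn nothing without a later event. Under the Section 16.1 wording, which censors at the last assessment of any kind, that same subject would get (253 − 43 + 1)/30.4375 = 6.93 months and count as a success.

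**Size.** Each reclassified subject moves DRR by 1/112 = 0.89 points. The exact lower limit is 30.2% at 44/112 and 29.4% at 43/112. One subject therefore changes exclusion of the 29.5% bound only at 44/112. From 45/112 it takes two, and from 50/112 it takes seven (50 − 43).

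The documents give no frequency of NE runs. If 1, 2, 3, 4 or 5 of 112 are assumed to be affected and the true DRR is lowered from 45% by that fraction, the probability of a lower limit above 30% falls from 0.9055 to 0.8695, 0.8249, 0.7714, 0.7096 or 0.6406.

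**The case against.** The strongest reply is that the text above Table 4 already governs. It censors events after two or more missing assessments, and NE can reasonably be read as missing, especially since the best-overall-response rule works with evaluable scans. That may well be the intent. But neither document says so, the table uses two different terms in the same row, and a programmer following the table would get the other answer.

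Second, an NE visit is not the same as a missed visit. Protocol 7.3 calls for a clinical and skin examination at each tumor assessment and treats new cutaneous lesions as diagnostic of progression, so progression may have been looked for. This stands in part: it would be wrong to say that an NE scan carries no information at all. The plan nevertheless declines to use NE results as a censoring date, and it gives no reason for treating them differently in the gap.

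Third, the IERC charter, which is not available here, may settle some cases. Section 16.2.4 cites it for determining the first progression date, not for the length of the gap.

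A reader might also infer that PFS and Kaplan-Meier duration of response are biased in the same way. They are not. DRR scores early censoring as failure; Kaplan-Meier does not. Starting the gap at the last adequate scan turns some observed events into censored times, and the direction of the resulting bias is not fixed.

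**Conclusion.** The point holds as an unclear rule with a one-sided risk for the primary DRR. On the literal wording of Table 4 and Table 11, some responders would count as durable who would be failures had the same scans been missed.

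Under Table 4 the reach is narrow. In year 1 it takes a confirmed responder with at least two consecutive NE scans, then PD or death, with the 6-month mark falling after the last adequate scan. The scan counts assume nominal visit weeks. Each such subject is worth 0.9 points of DRR.

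A reader might infer that any stretch without an evaluable scan counts as durable response, or that one subject decides whether the historical bound is excluded. The documents support neither. A single NE scan makes no difference, Table 4 gives no credit without a later event, and the one-subject case arises only at exactly 44/112. Excluding 29.5% is an illustration of precision in Section 7, not a success criterion. The number of affected subjects is unknown, so the probabilities for 1 to 5 subjects rest on an assumption. The sample-size and precision figures are correct and unaffected.

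**What to change.** 1. In both gap rows of Part B SAP Table 4 and protocol Table 11, start the gap at the *last adequate tumor assessment (or first dose, if none after baseline)*.
2. In Section 16.2.4, state that an NE or NA assessment counts as missing in the rule on two or more missing assessments.
3. In SAP Section 16.1 and, for Part B, in the duration-of-response text of protocol 8.3.2, change the censoring date to the last adequate assessment, to match SAP Section 16.2.3 and Table 4.

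The cost is a few phrases in two documents. The downside is that a few PD or death events after NE runs become censored in PFS and duration of response, and DRR may fall slightly.

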16.2.5 Response Status at 6 and 12 Months after Start of Study Treatment

The response status at 6 and 12 months after start of study treatment according to RECIST 1.1 and as determined by the IERC will be determined. A subject will be considered to be in response at the given time point (6 or 12 months after start of study treatment) if the subject had a documented response (PR or CR) prior to that time point, and did not have any of the following events up to the given time point:

- death
- documented disease progression according to RECIST 1.1
- lost to follow-up
- withdraw consent

The proportion of subjects with response at 6 and 12 months after start of study treatment will be calculated as the proportion of subjects in response among all subjects that have started study treatment at least 6 (12) months prior to the time of the analysis, respectively. Clopper-Pearson 95% CIs will be reported as well.

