7.1.5 Post Treatment Follow-up

Subjects with an ADR ongoing at the End-of Treatment visit must be followed up until the ADR resolves, becomes stable, or is considered not clinically significant by the Investigator. In addition, subjects will be followed for any AE suspected to be related to trial treatment, especially for the occurrence of new autoimmune events up to 3 months after the last dose of avelumab.

For subjects who discontinue treatment prior to Week 13, off-treatment interviews (optional for both Part A and Part B) will be scheduled for 13 weeks and 6 months from the start of treatment to collect subjects' current experience with their disease, the study drug, and their experience within the trial. In case of discontinuation later than Week 13 but prior to 6 months of treatment, an off-treatment interview (optional for both Part A and Part B) will be scheduled for 6 months from the start of treatment.

For Part A, subjects without PD at the End-of-Treatment visit will be followed up for disease progression until PD (CT / MRI scans every 6 weeks until Week 55 [12 months] after the first study drug administration, then every 12 weeks using the same procedures and review as while on treatment; for trial sites in Germany, only MRI is to be used). CCI [REDACTED]

For Part B, subjects without PD at the End-of-Treatment visit will be followed for disease progression until PD (CT / MRI scans every 6 weeks until Week 55 [12 months] after the first study drug administration, then every 12 weeks).

After the End-of-Treatment visit, subjects will be followed quarterly for survival (including assessment of any further tumor therapy). The survival follow-up will continue for up to 5 years after the last subject receives the last dose of avelumab or last subject dies, whichever occurs earlier (see Section 5.7 for details of the end of study).

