8.3.2 Secondary Endpoints

The duration of response will be calculated for each subject with a confirmed response as the time from first observation of response until first observation of documented disease progression or death within 12 weeks of the last tumor assessment, whichever occurs first.

For subjects with a confirmed response but neither documented disease progression nor death within 12 weeks after the last tumor assessment, as of the cut-off date for the analysis, the duration of response will be censored at the date of the last tumor assessment. Detailed censoring rules for duration of response can be found in [Table 9](#) for Part A and in [Table 11](#) for Part B.

The response status at 6 and 12 months after start of trial treatment according to RECIST 1.1 (as determined by the IERC) will be determined. A subject will be considered to be in response at the given timepoint (6 or 12 months after the start of the subject’s treatment) if the subject had a documented response (PR or CR) prior to that timepoint, and neither died nor experienced disease progression according to the RECIST 1.1 nor was lost to follow-up up to the given timepoint.

The PFS time, according to the RECIST 1.1, will be defined from first administration of trial treatment until first observation of PD or death within 12 weeks of the last tumor assessment or first administration of trial treatment (whichever is later). Details on determination of the first disease progression date will be specified in the IERC charter.

If a subject has neither a progression date nor a death date within 12 weeks after the last tumor assessment as of the data inclusion cut-off date for the analysis, the PFS time will be regarded as censored on the date of last known tumor assessment, or date of the first administration of trial treatment if the subject does not have any postbaseline tumor assessment. In Part B, PFS time will be regarded as censored on the date of last adequate tumor assessment (ie, having a result that is not non-evaluable or not available) if the subject begins a new anticancer therapy.

For Part A, subjects with both of the following conditions fulfilled, the general censoring rules apply as presented in [Table 9](#).

- Baseline tumor assessment
- At least one tumor assessment after start of treatment

Table 9 Part A: General Censoring Rules for Progression-free Survival and Duration of Response

		Date of event / censoring	Censoring

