16.1 Primary Endpoint Analyses

Analysis sets: ITT analysis set, PP analysis set

The primary endpoint is the confirmed BOR to therapy in terms of either CR or PR according to RECIST 1.1 (Appendix I), as determined by an IERC. The tumor response will be based on the IERC assessment of overall response at each time point. In case of different dates of scans within the same tumor assessment visit, the earliest scan date should be used as the date of tumor assessment.

The confirmed BOR is defined as the best response obtained among all tumor assessment visits after start of trial treatment until documented disease progression, excluding assessments after start of subsequent anticancer therapy, taking requirements for confirmation into account as detailed below. The confirmed ORR will be defined as the proportion of subjects with a confirmed BOR of PR or CR.

A separate Imaging Data Management Plan and Data Transfer Plan will be created to summarize the details of the data structure and data delivery schedule of IERC assessment results.

The following requirement is taken into account for confirmation of response:

- PR or CR needs to be confirmed at a subsequent tumor assessment, preferably 6 weeks after the initial observation of response and according to the normal 6-week assessment schedule but no sooner than 5 weeks after the initial documentation of CR or PR.
- PR can be confirmed at an assessment later than the next assessment after the initial documentation of PR.
- The minimum duration for a BOR of SD is defined as at least 6 weeks after start of study treatment.

Table 2 summarizes the derivation rules described by [Eisenhauer, et al.](#) for the BOR when conformation from subsequent assessment is needed (5).

Table 2 Best overall response when confirmation of CR/PR is required

| Overall response 1st time point | Overall response subsequent time point | Best overall response (BOR) |
|---------------------------------|--|-----------------------------|
| CR | CR | CR |
| CR | PR | SD, PD or PR ^a |

| Overall response 1st time point | Overall response subsequent time point | Best overall response (BOR) |
|--|---|---|
| CR | SD | SD provided minimum criteria for SD duration met; otherwise, PD |
| CR | PD | SD provided minimum criteria for SD duration met; otherwise, PD |
| CR | NE | SD provided minimum criteria for SD duration met, otherwise NE |
| PR | CR | PR |
| PR | PR | PR |
| PR | SD | SD |

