| PR | PD | SD provided minimum criteria for SD duration met, otherwise, PD |
| PR | NE | SD provided minimum criteria for SD duration met, otherwise NE |
| NE | NE | NE |

CR = complete response, PR = partial response, SD = stable disease, PD = progressive disease, NE = in-evaluable.

^a If a CR is truly met at first time point, then any disease seen at a subsequent time point, even disease meeting PR criteria relative to baseline, makes the disease PD at that point (since disease must have reappeared after CR). Best response would depend on whether minimum duration for SD was met. However, sometimes 'CR' may be claimed when subsequent scans suggest small lesions were likely still present and in fact the subject had PR, not CR at the first time point. Under these circumstances, the original CR should be changed to PR and the best response is PR.

The analysis of the primary endpoint will be conducted for the ITT analysis set. The test statistic of the exact binomial test will be calculated and compared with the thresholds given in Section 7 to determine whether the null hypothesis of an $ORR \leq 20\%$ can be rejected at the interim analysis, or, if not rejected at the interim, at the primary analysis. The thresholds given in Section 7 were chosen based on the binomial distribution:

- The binomial probability of 20 or more responses in 56 subjects under a true response rate of 20% is 0.0045.
- In case of an ITT population of 88 patients, the binomial probability of 26 or more responses in 88 subjects under a true response rate of 20% is 0.0211.
- In the case of 88 patients, the probability of rejecting the null hypothesis in the interim or the primary analysis, given a true response rate of 20%, is 0.0211, obtained via the exact calculation described in Jennison and Turnbull(1), Section 12.1.2, Formula 12.5-12.7. The associated confidence interval would not include 20%. If the ITT population would not be 88 patients, the calculation of the rejection boundaries would still be by Jennison and Turnbull (1).

Therefore, the overall Type I error rate is controlled at a level of 2.5% (one-sided).

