14.2 Subsequent Anti-Cancer Therapies/Procedures

Subsequent anti-cancer treatment will be provided in a data listing with data retrieved from “Anti-Cancer Treatment after Discontinuation Details”, “Radiotherapy after Discontinuation”, and “Surgery after Discontinuation” eCRF pages. The earliest date of start of new anti-cancer *drug* therapy will be used for the definition of the on-treatment period; the earliest date of start of any new anti-cancer therapy will be used for censoring for efficacy analyses.

15 Treatment Compliance and Exposure

Analysis sets: FAS / Safety analysis set

All dosing calculations and summaries will be based on “Avelumab Administration Details” eCRF pages.

Subjects will receive an IV infusion of avelumab at a dose of 10 mg/kg (over the duration of 1 hour [-10 minutes / +20 minutes, that is, over 50 to 80 minutes]) once every 2 weeks (one cycle). Analysis of exposure will be based on the calculated actual dose levels (total dose administered/weight, mg/kg). The last available weight of the subject within 3 days prior to the day of dosing will be used.

In case of missing total dose, the dose level as entered in the eCRF will be used.

The duration of therapy (in weeks) during the study is defined as:

$$\text{duration} = \left(\frac{\text{date of last dose} - \text{date of first dose} + 14}{7} \right)$$

The cumulative dose (mg/kg) per subject in a time period is the sum of the actual dose levels that the subject received within that period (i.e. total dose administered (mg) / weight (kg)).

Each cycle is defined by a 2-week period. The dose intensity and the relative dose intensity will be calculated for each subject across all cycles. The dose intensity (mg/kg/cycle) per cycle is defined as

$$\text{dose intensity} = \left(\frac{\text{Cumulative dose}}{(\text{duration of therapy (in weeks)})/2} \right)$$

The relative dose intensity is defined as the actual dose intensity divided by the planned dose per cycle.

The summary of treatment exposure and compliance table will include the following information:

- Duration of therapy (weeks)
- Total number of infusions received
- Cumulative dose of therapy (mg/kg)
- Dose intensity (mg/kg/cycle)
- Relative dose intensity of therapy (%)

A listing of treatment exposure and compliance will also be created to summarize the information listed above for each subject.

Partial Doses

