16.2.2 Best Overall Response and Objective Response

The confirmed BOR is defined as the best confirmed response obtained among all tumor assessment visits after start of study treatment until documented disease progression, taking requirements for confirmation into account as detailed in [Section 16.1.1](#). In addition, the minimum duration for a BOR of SD is defined as at least 6 weeks after start of study treatment. A BOR of PD requires that progression is observed ≤ 12 weeks after first dose of study treatment (and not qualifying for CR, PR or SD).

Only tumor assessments performed before the start of any further anti-cancer treatment will be considered in the assessment of BOR. Clinical deterioration will not be considered as documented disease progression. If a tumor assessment was performed on the same day as the start of a new anti-cancer therapy, it is assumed that the tumor assessment was performed prior to the start of the new anti-cancer therapy; therefore, this tumor assessment is included in the assessment of BOR.

The tumor response at each assessment visit will be determined according to RECIST 1.1 and as adjudicated by an IERC. In case of different dates of scans within the same tumor assessment visit, the date of assessment is determined by the IERC as specified in the Charter.

The objective response rate (ORR) is defined as the proportion of subjects having reached a confirmed BOR of CR or PR according to RECIST 1.1 and as determined by the IERC.

[Table](#) summarizes the derivation rules described by [Eisenhauer, et al.](#) for the BOR when confirmation from subsequent assessment is needed (5).

Table 3 Best Overall Response When Confirmation of CR/PR Is Required

| Overall response 1st time point | Overall response subsequent time point | Best overall response (BOR) |
|------------------------------------|---|---|
| CR | CR | CR |
| CR | PR | SD, PD or PR ^a |
| CR | SD | SD provided minimum criteria for SD duration met; otherwise, PD |
| CR | PD | SD provided minimum criteria for SD duration met; otherwise, PD |
| CR | NE | SD provided minimum criteria for SD duration met, otherwise NE |
| PR | CR | PR |
| PR | PR | PR |
| PR | SD | SD |
| PR | PD | SD provided minimum criteria for SD duration met, otherwise, PD |
| PR | NE | SD provided minimum criteria for SD duration met, otherwise NE |
| NE | NE | NE |

CR = complete response, PR = partial response, SD = stable disease, PD = progressive disease, NE = non-evaluable.

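### Response status at 6 and 12 months accepts an unconfirmed response and does not end at new anti-cancer therapy, so it can count subjects who are non-responders in the ORR

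*SAP*

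**What the plan says.** **Landmark endpoint.** Part B SAP 16.2.5 and Part A SAP 16.2.4 count a subject as in response at 6 or 12 months "if the subject had a documented response (PR or CR) prior to that time point, and did not have any of the following events". The list that follows has four entries: death, documented progression, loss to follow-up and withdrawal of consent. Protocol 8.3.2 counts a subject who "had a documented response (PR or CR) prior to that timepoint, and neither died nor experienced disease progression" and was not lost to follow-up. The proportion is taken "among all subjects that have started study treatment at least 6 (12) months prior to the time of the analysis".

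**ORR.** Part A SAP 16.1 defines best overall response (BOR) "excluding assessments after start of subsequent anticancer therapy, taking requirements for confirmation into account as detailed below". Part B SAP 16.2.2 also requires confirmation and adds: "Only tumor assessments performed before the start of any further anti-cancer treatment will be considered in the assessment of BOR". In both BOR tables (Part A Table 2, Part B Table 3), PR followed by SD gives SD. For PR followed by NE the entry is "SD provided minimum criteria for SD duration met, otherwise NE".

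**Other response endpoints.** Duration of response is defined only for confirmed responders, so the durable response rate (DRR) rests on confirmation too. Time to response (16.4.1 in both SAPs) says explicitly that the response must later be confirmed.

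**New therapy.** Part B SAP 14.2 says that "the earliest date of start of any new anti-cancer therapy will be used for censoring for efficacy analyses". Part A SAP 14.2 uses the date of new drug therapy only to define the on-treatment period.

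**The concern.** The landmark rate will be read beside the ORR as the share of subjects still responding at 6 or 12 months. Protocol 5.2, in the Part A design discussion, names it with duration of response, PFS and OS as a way to judge whether the ORR reflects lasting benefit. That reading needs the landmark responders to be drawn from the ORR responders, and the rule as written does not ensure this.

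There are two separate gaps:

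1. One unconfirmed PR or CR is enough to qualify.
2. Starting another anti-cancer treatment does not end the response. A response first seen on that treatment can count, and time spent on it can count as response to avelumab.

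In Part B, durability is carried by the primary DRR, and this looser rate is reported next to it. At the specified Part B interim the DRR is not analysed but this endpoint is (Part B SAP 8.2).

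**Working it through.** The documents give no figure for this endpoint, so the check applies the two written rules to the same subjects and then sizes one misclassified subject.

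**Step 1. Rules applied to example subjects at 6 months.** Scheduled scans fall on Days 43, 85, 127 and 169. Six months is 6 × 30.4375 = 182.6 days. No example subject has progression, death, loss to follow-up or withdrawn consent.

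| Subject | IERC sequence | ORR | Landmark |
|---|---|---|---|
| A | PR Day 43; SD Days 85, 127, 169 | Non-responder (PR then SD = SD) | In response |
| B | PR Day 43; NE at every later scan | Non-responder (SD or NE) | In response |
| C | SD Days 43, 85; new therapy; PR Days 127, 169 | Non-responder (PR scans excluded) | In response |
| D | SD Day 43; PR Day 85; new therapy; PR Days 127, 169 | Non-responder (confirming scan excluded) | In response |
| E | PR Days 43, 85; new therapy; no progression | Responder | In response |

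A and B show the confirmation gap, which proves the point without any appeal to new therapy. C and D show the new-therapy gap. Their later scans can exist because scanning continues after treatment: "For Part B, subjects without PD at the End-of-Treatment visit will be followed for disease progression until PD". Protocol 7.1.5 has a matching rule for Part A. Subject E does not break the subset relation, but time on another treatment is counted as response.

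**Step 2. Direction.** Each gap admits subjects whom a stricter rule would leave out, and the denominator does not change. The rate can only go up.

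**Step 3. Size per affected subject.**

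- Part B primary analysis, N = 112 (planned size; the cut-off is 15 months after the last start, so all subjects qualify at both time points): 1/112 = 0.89 points.
- Part A 6-month rate, N = 88 (actual enrolment, Part A SAP section 7): 1/88 = 1.14 points.
- Part A 12-month rate at the primary analysis: the denominator is smaller and not given. Assuming 44 to 88 subjects, 1/44 = 2.27 down to 1.14 points.
- Part B specified interim: the cut-off is 3 months after the 25th subject starts. Six months of follow-up needs a start at least 3 months before the 25th, so at most 24 subjects qualify: 1/24 = 4.17 points or more.

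**Step 4. Assumed range.** With 1 to 3 affected subjects, the excess is 0.89 to 3/112 = 2.68 points in Part B, and 1.14 to 3/88 = 3.41 points in the Part A 6-month rate. The count is an assumption.

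**The case against.** **Part B SAP 14.2 already covers new therapy.** This is partly right: it states a general rule for efficacy analyses. But 16.2.5 is a yes/no proportion. It does not refer to 14.2 and does not say whether a subject cut off by new therapy is a success or a failure. Protocol 8.3.1 and Part B SAP 16.1 do say this for censored durations in the DRR. Section 14.2 says nothing about confirmation. In Part A there is no such rule, and duration of response and PFS are not censored at new therapy either, so the Part A mismatch is with BOR and ORR only.

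**The sponsor revisited this definition on purpose.** Item 11 of the version 3.0 changes in the Part A SAP restored the text of SAP version 1 for this section. That reversal concerned a condition about evaluable assessments and did not address confirmation.

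**Nothing requires the landmark responders to be a subset of the ORR responders.** True, and an unconfirmed landmark could be chosen deliberately. The plan gives no sign of that choice, and the use stated in protocol 5.2 works poorly without the subset.

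**Durability is reported elsewhere on confirmed responses.** This stands. Kaplan-Meier duration of response covers confirmed responders in both parts, and a DRR is reported in both. It limits the importance of the point.

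**Paths C and D are probably rare, and the count is assumed.** Both remarks stand. Only the per-subject arithmetic is firm.

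**The remedy uses data after the landmark.** This also stands: a first PR on Day 169 followed by progression on Day 211 would become not in response at 6 months. The ORR treats that subject the same way. The remedy also does not require an evaluable scan close to the landmark, which is a separate matter.

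**Conclusion.** The concern holds. As written, response status at 6 and 12 months can include subjects whom the same plan classes as non-responders, and it counts time on another anti-cancer treatment as response. The inconsistency follows from the definitions alone. Its numerical effect depends on a count the documents do not give: 0.9 points per subject in Part B at the primary analysis, 1.1 points in the Part A 6-month rate, and at least 4.2 points in the 6-month rate at the specified exploratory Part B interim. The endpoint is secondary and untested, and neither primary endpoint changes. The definition should be corrected, but no confirmatory conclusion depends on it.

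**What to change.** In Part B SAP 16.2.5 and protocol 8.3.2, define in response at 6 (12) months as a confirmed CR or PR by the IERC, first documented before the time point, with none of these up to the time point: death, progression, loss to follow-up, withdrawn consent, or start of any new anti-cancer therapy (dated as in Part B SAP 14.2). State that a subject with any of these events counts as not in response. Keep the present denominator. In Part A, whose results the protocol already cites as published, report this definition as a sensitivity analysis.

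The change is to wording only, although the protocol text needs an amendment. The reported rate will be slightly lower, and a few late first responses may not be confirmable by the cut-off, a limit the ORR already has:

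- **Part B.** Fifteen months is 456.6 days, so the cut-off for the last-enrolled subject is about Day 457. Scheduled scans late in the first year fall on Days 337 and 379, then Day 463. With the 5-week minimum, a first response up to Day 379 − 35 = 344 can be confirmed on Day 379. A first response at an unscheduled scan on Days 345 to 365, or an NE scan on Day 379, would wait for Day 463. On schedule this affects only subjects who started within about 463 − 457.6 = 5.4 days of the last one.
- **Part A.** At the 6-month cut-off (about Day 183 for the last subject), a first response on Day 169 would be confirmed on Day 211. This affects subjects who started within about 211 − 183.6 = 27.4 days of the last one, which is a further reason to use a sensitivity analysis there.
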